4.1.1. Inclusion Criteria – Part 1 (Treatment Period)

Prospective participants must meet all of the following criteria during the pre-study evaluation in order to be eligible to enroll in the study:

Part 1 (Treatment Period) Participant Category Inclusion Criteria:

1. Prospective participant meets all of the following criteria specific to their applicable participant category:

Participant Category 1: *GRN* Mutation Carriers, Symptomatic, from AL001-1

- Completed Study AL001-1 through the Day 57 visit and did not experience AEs that the investigator deems would prevent safe participation in Study AL001-2.
 - All previous participants in the AL001-1 study must be rescreened and meet all inclusion/exclusion criteria applicable to this study.
- Meets 1 or more of the 6 behavioral/cognitive symptoms required for a diagnosis of possible behavioral variant frontotemporal dementia (bvFTD; [Rascovsky 2011](#)), or has a diagnosis of PPA ([Gorno-Tempini 2011](#)).

Participant Category 2: *GRN* Mutation Carriers, Asymptomatic, from AL001-1

- Prospective participant completed Study AL001-1 through the Day 43 visit and did not experience AEs that the investigator deems would prevent safe participation in Study AL001-2.
 - All previous participants in the AL001-1 study must be rescreened and meet all inclusion/exclusion criteria applicable to this study. If a participant becomes symptomatic during or after Study AL001-1, they will be screened under Category 3 (symptomatic).

Participant Category 3: GRN Mutation Carriers, Symptomatic, New

- Is a carrier of a loss-of-function *GRN* mutation causative of FTD and knows their mutation status.
- Has a CDR® plus NACC FTLD global score of 0.5, 1, or 2; and 1 or more of the 6 behavioral/cognitive symptoms required for a diagnosis of possible bvFTD ([Rascovsky 2011](#)), or a diagnosis of PPA ([Gorno-Tempini 2011](#)).

Participant Category 4: C9orf72 Mutation Carriers, Symptomatic, New

- Is a carrier of a hexanucleotide repeat expansion *C9orf72* mutation causative of FTD and knows their mutation status.
- Has a CDR® plus NACC FTLD global score of 0.5, 1, or 2; and 1 or more of the 6 behavioral/cognitive symptoms required for a diagnosis of possible bvFTD ([Rascovsky 2011](#)), or a diagnosis of PPA ([Gorno-Tempini 2011](#)).

Part 1 (Treatment Period) General Inclusion Criteria:

2. 18 to 85 years of age, inclusive, at screening.

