7.1. Definitions of Adverse Events

The investigator is responsible for reporting all AEs that are observed or reported during the study, regardless of their relationship to study drug or their clinical significance.

An AE is defined as any untoward medical occurrence in a participant enrolled into this study regardless of its causal relationship to study drug. Participants will be instructed to contact the investigator at any time after informed consent signature if any symptoms develop. Study participants should be instructed to report all AEs to the investigator. All AEs must be appropriately documented in the participant's original source documents and on the eCRFs. Investigators should report the diagnosis rather than list symptoms, whenever possible.

An AE does not include the following:

- Elective medical or surgical procedures planned prior to the start of study treatment (e.g., hip replacement surgery) that did not result from a worsening of a previous condition. The condition that led to the procedure may be an AE and must be reported.
- Pre-existing diseases, conditions, or laboratory abnormalities present or detected at the screening visit that do not worsen.
- Situations where an untoward medical occurrence has not occurred (e.g., hospitalization for study drug administration per institutional guidelines, elective surgery, social and/or convenience admissions).
- Overdose without clinical sequelae.
- Any medical condition or clinically significant laboratory abnormality that has an onset date before the consent form is signed and that is not related to a protocol-associated procedure is not an AE. It is considered to be a pre-existing medical condition and should be documented on the medical history eCRF. However, deterioration of a medical condition or new or worsened clinically significant abnormality during the study should be reported as an AE.
- Any AE that began during the Phase 1 study (AL001-1) and was ongoing at the time of enrolling in this study (AL001-2) will not be considered an AE, but medical history.

Adverse events resulting from concurrent illnesses, reactions to concurrent illnesses, reactions to concurrent medications, or progression of disease states must also be reported in the established time frames.

A treatment emergent adverse event (TEAE) is defined as any event not present before exposure to study drug, or any event already present that worsens in either intensity or frequency after exposure.

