8.1. Sample Size Estimations

Part 1 (Treatment Period)

The primary objective of Part 1 of the study is to assess the safety profile of repeat dosing of AL001 in asymptomatic and symptomatic participants. Descriptive statistics will be used to assess clinically significant associated findings (for example, study drug related AEs leading to study drug discontinuation or study drug-related SAEs). The Part 1 sample size of 40 participants was chosen based on feasibility; however, the probability of detecting at least 1 clinically significant associated finding will be explored. When the probability of a clinically significant associated finding for a single participant is 0.1%, 1%, 5%, and 10%, then with a sample size of 40 participants, the probability of detecting at least 1 clinically significant associated finding across all participants is 3.9%, 33.1%, 87.1% and 98.5% respectively.

Part 2 (Optional OLE)

It is estimated that up to 40 participants from Part 1 of the study will be eligible to continue with Part 2 of the study. Part 2 is optional for participants, and at the discretion of the investigator.

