Baseline will be defined as the last non-missing assessment, including repeated and unscheduled measurements, prior to the start of first study drug administration.

Due to the high rate of participant attrition over the study duration and small FTD cohort sizes, time points beyond week 49 will not be included in the cohort level summary of the figures.

All CIs will be 2-sided and performed using a 5% significance level except for PK parameters for which, 90% CI and geometric mean will be used. All p-values will be presented to 3 decimal places and values less than 0.001 or greater than 0.999 will be presented as <0.001 and >0.999, respectively. As the objectives of the study are exploratory in nature no adjustments for multiplicity will be made.

No formal significance testing will be performed.

Analysis visit windows will be applied for COA and Biomarker analysis. A detailed explanation about the analysis visit windows will be described in the specific section of each analysis,

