2.1. Sample Size

Part 1 (Treatment Period)

The primary objective of Part 1 of this study is to assess the safety profile of repeat dosing of AL001 in three FTD cohorts: aFTD-*GRN*, FTD-*GRN*, and FTD-*C9orf72* participants.

Descriptive statistics will be used to assess clinically significant associated findings (for example, study-drug related AEs leading to study drug discontinuation or study-drug related SAEs). The Part 1 sample size of 40 participants was chosen based on feasibility; however, the probability of detecting at least 1 clinically significant associated finding will be explored. When the probability of a clinically significant associated finding for a single participant is 0.1%, 1%, 5%, and 10%, then with a sample size of 40 participants, the probability of detecting at least

1 clinically significant associated finding across all participants is 3.9%, 33.1%, 87.1%, and 98.5%, respectively.

Part 2 (Optional OLE)

It is estimated that up to 40 participants from Part 1 of the study will be eligible to continue with Part 2 of the study. Part 2 is optional for participants, and at the discretion of the investigator.

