2.3.2. Safety Analysis Population

The safety analysis population will consist of all participants who received at least 1 dose of AL001. The safety analysis population will be used for all safety and COA summaries.

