Adverse Events will be coded by SOC and PT according to MedDRA, version to be delineated in the CSR.

All summary tables will include counts and frequency of participants and number of events. Subject incidence rate of AEs will be summarized by SOC and PT and for PT only. The summary will be provided separately by overall descending incidence rate and then by alphabetical order. A separate summary will be provided by alphabetical order for SOC and PT. A participant with 2 or more occurrences for the same AE, the subject will be counted only once in that level using the worst severity (for the severity table) or the most related (for the relationship to study drug table). Percentages will be based upon the number of participants in the Safety population.

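### Crude AE percentages in SAP 6.1 mix drug risk with length of follow-up and with earlier AL001 treatment; add exposure-adjusted incidence and a prior-exposure split

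*SAP*

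**What the plan says.** SAP 2.3.2 defines the safety set: "The safety analysis population will consist of all participants who received at least 1 dose of AL001". SAP 6.1 uses it as the denominator: "Percentages will be based upon the number of participants in the Safety population". Event counts are added ("All summary tables will include counts and frequency of participants and number of events"), but there is no person-time rate, no time-to-event estimate and no breakdown by earlier AL001 treatment. SAP 5.3 derives each participant's duration of exposure, but only for the exposure table.

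SAP section 2 combines Parts 1 and 2, whereas Protocol 8.4 presents Part 2 on its own. The same SAP section removes time points after Week 49 from the cohort-level figures, with the reason: "Due to the high rate of participant attrition over the study duration and small FTD cohort sizes". It gives no attrition rate and makes no matching provision for AE incidence.

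Protocol 1.2.2.1 reports 6 asymptomatic and 8 symptomatic GRN carriers dosed in AL001-1. Under Protocol 3.1, asymptomatic participants can come only from that study, and the C9orf72 cohort is all new. Under Protocol 4.1.1, a Phase 1 carrier may enter if he or she "did not experience AEs that the investigator deems would prevent safe participation in Study AL001-2". Protocol 7.1 adds that an event which began in AL001-1 and "was ongoing at the time of enrolling in this study (AL001-2) will not be considered an AE, but medical history".

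Table 1 of both documents says the primary safety endpoints will be evaluated by dose, for example by tertiles of the weight-normalised dose received. SAP section 6 gives no method for this, and SAP section 12 does not record dropping it.

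**The concern.** AE incidence comes first among the primary safety endpoints. A percentage of everyone dosed answers a clear question only if participants are watched for similar lengths of time. Here one participant may receive a single infusion and another 50. A cohort that leaves early can look safer than one that stays, and a cohort that continues through Part 2 can look worse, with no difference in risk per unit of time.

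Earlier AL001 treatment adds a second layer. It separates aFTD-GRN from FTD-C9orf72 completely and is mixed within FTD-GRN and All Participants. Hypersensitivity is the class risk named in Protocol 1.3.1, and Protocol 1.3.2 reports that treated subjects have developed anti-drug antibodies. First and repeat exposure could therefore plausibly carry different risks, in either direction, and a single column cannot show it.

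**Working it through.** **The plan's own figure.** SAP 2.1 says "The Part 1 sample size of 40 participants was chosen based on feasibility", and Protocol 8.1 gives the chance of at least one finding: "across all participants is 3.9%, 33.1%, 87.1% and 98.5% respectively". With 1 − (1 − p)^40 and p = 0.1%, 1%, 5% and 10%, the results are 3.92%, 33.10%, 87.15% and 98.52%. The stated figures reproduce.

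**Exposure times.** SAP 5.3 counts from first dose to last dose plus 28 days. Study days come from the schedules of assessments.
- One dose: 28 days
- Last dose at Week 49 (Day 337): 336 + 28 = 364 days
- Last dose at Week 97 (Day 673): 672 + 28 = 700 days
- Last dose at Week 197 (Day 1373): 1372 + 28 = 1400 days

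**Same hazard, different exposure.** Assume a constant hazard h and a 10% risk over full Part 1 exposure; neither is in the documents. Then h = −ln(0.90)/700 per day, and the crude risk at t days is 1 − exp(−h·t): 5.3% at 364 days, 10.0% at 700 and 19.0% at 1400. The ratios are 10.0/5.33 = 1.9 and 19.0/5.33 = 3.6. Assumed 96-week risks of 5%, 20% and 30% give ratios of 1.9, 1.8 and 1.8 (364 against 700 days) and 3.7, 3.3 and 3.0 (364 against 1400 days).

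**Direction within one cohort.** Let a fraction a leave after the Week 49 dose, still with a 10% 96-week risk.

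| a (assumed) | Others stop at Week 97 | Others complete Part 2, parts combined |
|---|---|---|
| 25% | 8.83% | 15.58% |
| 50% | 7.67% | 12.17% |
| 75% | 6.50% | 8.75% |

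For example, 0.25 × 5.33 + 0.75 × 19.0 = 15.58. The crude figure falls below or above 10% depending on who stays.

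**What a person-time rate does.** In the constant-hazard example, the expected rate is h × 365.25 × 100 = 0.10536/700 × 36,525 = 5.5 per 100 participant-years in every group, whatever its exposure. For an event that happens only at the first infusion, with 10% probability, the position reverses. The crude figure is 10% in both groups, but the rate is 0.10/(0.90 × 364/365.25) = 11.1 per 100 participant-years at 364 days and 0.10/(0.90 × 1400/365.25) = 2.9 at 1400 days.

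**Earlier treatment.** The ceiling is 6 + 8 = 14, which is 35% of 40 and 70% of the 20 GRN places. If previously treated participants carry r times the risk of naive ones, the All Participants percentage is (26 + 14r)/40 of the naive risk: 0.65 at r = 0, 0.825 at r = 0.5, 1.00 at r = 1 and 1.35 at r = 2. For an assumed FTD-GRN column of 8 previously treated and 20 − 14 = 6 naive, (6 + 8r)/14 gives 0.43, 0.71, 1.00 and 1.57. The documents do not give r.

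**The case against.** The strongest reply is that this is a small, single-arm, descriptive study sized on feasibility, with no formal testing and no planned contrast of AE rates between cohorts. Exposure is not ignored: duration, doses and total dose are summarised, events are counted, and tertiles of dose are promised. Summaries are shown by cohort, so mixing by earlier treatment is confined to FTD-GRN and All Participants. Participants who stop drug in Part 1 are encouraged to stay to Week 97, and AEs are collected to the end-of-study or safety follow-up visit, so short dosing need not mean short observation.

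Much of this stands, and it limits the point. It does not remove it, because percentages set side by side will be read comparatively. An exposure table and event counts on separate pages do not give a rate. At 60 mg/kg every 4 weeks, cumulative dose largely tracks time on treatment, so crude percentages by tertile could rise with follow-up even at constant risk.

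Four stronger readings are tempting, and the documents do not support them:
- *The percentages understate risk.* The table shows that combining Part 2 can push them up.
- *Phase 1 carriers are a group selected for tolerance.* The criterion only bars disqualifying AEs. Protocol 1.2.2.1 reports that all 14 completed dosing with no dose-limiting AEs, so the documents show nobody excluded for intolerance.
- *Detection probabilities should be restated for 26 naive participants.* That needs all 14 to enroll and to carry no risk. The stated figures concern findings under repeat dosing in all 40 and are arithmetically correct.
- *AEs carried over from AL001-1 disappear.* Worsening still counts as treatment-emergent, and SAP 4.3 summarises and lists medical history.

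**Conclusion.** The point holds as a cheap improvement to the primary safety readout, not as an error in the stated figures. Crude percentages in SAP 6.1 depend on length of observation as well as drug risk, in either direction, and are not reliably comparable across cohorts. Under a constant hazard and assumed 96-week risks of 5% to 30%, exposure alone can produce differences of about 1.8- to 3.7-fold between cohorts with the same hazard. These sizes also rest on assumed drop-out at Week 49 and on treating exposure time as time at risk. Continued AE collection after stopping drug would narrow them. Earlier AL001 treatment is confounded with cohort and mixed in two columns. Its effect on apparent risk cannot be signed from the documents, and 14 is a ceiling rather than the number enrolled.

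**What to change.** In SAP 6.1, keep the percentages and add:
- **Exposure-adjusted incidence** by cohort for TEAEs, SAEs and TEAEs leading to study drug discontinuation: participants with a first event per 100 participant-years at risk. Time at risk ends at the first event or at the end of AE collection. The SAP must name that end, because Protocol 1.3.4 says 8 weeks after the last dose while Protocol 6.5.1 says the later of the end-of-study and safety follow-up visits. SAP 5.3 exposure duration is not the same quantity and should not be substituted without saying so.
- **Early-onset events** such as infusion reactions: a statement that the crude percentage remains the main measure, because a person-time rate dilutes them.
- **Prior-exposure split**: AL001-naive and previously treated columns within FTD-GRN and All Participants. Define the split by actual dosing in AL001-1, not by participant category, because Protocol 4.1.1 screens asymptomatic Phase 1 participants who become symptomatic under Category 3.
- **Dose tertiles**: a method for the evaluation promised in Table 1, using the same person-time rate. It remains descriptive, since someone who stops early because of an AE falls in a low tertile.

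The cost is a few table columns from dates already collected, with no change to conduct. The downsides are very small columns with unstable rates, and a rate that is easiest to interpret when the hazard is roughly constant. Protocol 8.1 and SAP 2.1 need no change on this point.

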6.1.1. Incidence of Adverse Events

An overall summary of AEs will be presented and will include summaries for the following:

- Any TEAE
- Any Treatment-Related TEAE
- TEAEs by Severity
- Treatment-Related TEAEs by Severity
- Any SAE
- Any Treatment-Emergent SAE
- Any Treatment-Related TESAE
- Any TEAE Leading to Study Drug Discontinuation
- Fatal TESAE

In addition, all TEAEs will be summarized by SOC and PT.

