4.3.2. Withdrawal From Study (Part 1)

A participant may be discontinued from the study (including study drug and all assessments) at any time if the participant or the investigator feels that it is not in the participant's best interest to continue. The following is a list of possible reasons for study discontinuation:

1. Participant withdrawal of consent
2. Lost to follow-up
3. Discretion of the investigator
4. Administrative or other reasons (e.g., premature termination of the study by Alector)

All Part 1 participants who discontinue the study drug and all assessments prior to the scheduled Week 97 visit should be encouraged to return to the site for a Part 1 EOS visit. Part 1 EOS assessments should be completed as soon as possible after the decision is made. A Safety Follow-Up visit will be performed 10 weeks after the participant's last study drug administration. Reasonable attempts will be made by the investigator to obtain reasons for participant withdrawals (e.g., 2 documented telephone calls on different days, followed by 1 registered letter). The reason for the participant's withdrawal from the study will be specified in the participant's source documents and in the eCRF.

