8.4. Statistical Analysis Methodology

The main statistical analysis will be performed on Part 1. The statistical analysis will be performed using SAS software Version 9.4 or later (SAS Institute Inc., Cary, North Carolina, USA). The statistical methods for this study will be described in a detailed Statistical Analysis Plan (SAP), which will be finalized before locking of the database. Changes from analyses planned in this protocol will be documented in the SAP. Any deviations from the planned analysis as described in the SAP will be justified and recorded in the final clinical study report (CSR).

For categorical variables, frequencies and percentages will be presented. Continuous variables will be summarized using descriptive statistics (number of participants, mean, standard deviation [SD], median, minimum, maximum, and 95% confidence interval [CI] where applicable). All summaries will be presented by combined participant status and dementia type at baseline (aFTD-*GRN*, FTD-*GRN* [bvFTD and PPA], FTD-*C9orf72* [bvFTD and PPA], and All Patients).

Part 1 (Treatment Period)

In Part 1, data collected for participants who failed screening and were not enrolled will not be presented in any summaries or data listings. All other data will be listed in data listings. Baseline will be defined as the last non-missing assessment, including repeated and unscheduled measurements, prior to the start of first study drug administration.

In Part 1, all CIs will be 2-sided and performed using a 5% significance level, except for PK parameters, for which 90% CI and geometric mean will be used. As the objectives of the study are exploratory in nature no adjustments for multiplicity will be made.

No formal significance testing will be performed.

Part 2 (OLE)

For Part 2, no formal statistical testing will be performed. Descriptive statistics will be presented for Part 2 separately from Part 1. The purpose of the OLE is to collect continued long-term (up to 96 weeks) safety and tolerability data from participants who have completed Part 1 of the study. As the objectives of the OLE are exploratory in nature no adjustments for multiplicity will be made.

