8.4.2.4. Adverse Events

Adverse events will be recorded as described in [Section 7.7](#) and will be coded to system organ class and preferred term according to MedDRA, Version 21.1 or later. A TEAE is defined as described in [Section 7.1](#). The following AE summaries will be reported by system organ class, preferred term, and combined participant status and dementia type at baseline:

- TEAEs
- Treatment-related TEAEs
- TEAEs by relationship to study drug
- TEAEs by severity
- SAEs
- TEAEs leading to study drug discontinuation
- TEAEs leading to study discontinuation

For safety reporting, any clinically significant changes in MRI after dosing relative to baseline will be evaluated by the investigator and will be included in the eCRF as AEs. A separate analysis of AEs identified through MRI will not be conducted.

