1.1. Objectives and Endpoints

Table 1: Part 1 (Treatment Period): Study Objectives and Endpoints

	Objective(s)	Endpoint(s)
Primary	The primary objective of the treatment period of the study is to evaluate the safety and tolerability of IV administration of AL001 over 96 weeks in asymptomatic and symptomatic carriers of a GRN mutation causative of FTD and in symptomatic carriers of a C9orf72 mutation causative of FTD.	Primary Safety Endpoints: To assess the potential effect of cumulative exposure on the safety profile of AL001, the following will be evaluated by dose, such as by using tertiles of the actual dose (normalized to weight) received: 
• Incidence, nature, and severity of AEs and SAEs• Incidence of treatment discontinuations and study discontinuations due to AEs• Physical examination abnormalities• Neurological examination abnormalities• Changes in vital signs from baseline over time• Changes in ECGs from baseline over time• MRI abnormalities after dosing relative to baseline• Changes in clinical laboratory tests from baseline over time• Sheehan Suicidality Tracking Scale (Sheehan-STS)• Incidence of ADAs to AL001
Secondary	The secondary objectives of the treatment period of the	

	
study are to evaluate the effect of IV administration of AL001 over 96 weeks in asymptomatic and symptomatic carriers of a GRN mutation causative of FTD and in symptomatic carriers of a C9orf72 mutation causative of FTD on the following:
	
	
Secondary PK Objective:
 
 • PK 	
Secondary PK Endpoints:
 
 • Serum concentration of AL001 at specified time points • AL001 PK parameters (if data permit) ◦ C_{max} ◦ C_{trough} ◦ AUC_{ss}
	
Secondary PD Biomarker Objectives:
 
 • Longitudinal plasma and CSF PGRN concentration levels • Longitudinal levels of Sortilin in WBCs 	
Secondary PD Biomarker Endpoints:
 
 • The overall change from baseline in PGRN in CSF • The overall change from baseline in PGRN in plasma • The overall change from baseline in Sortilin in WBCs in plasma

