3.1. Disposition

Participant disposition will be summarized. The number of participants and reasons for study discontinuation, reasons for study drug discontinuation, and the number of participants in each analysis population will be presented.

Participant disposition data and membership in analysis populations for participants in the Enrolled population will be presented in data listings.

Data collected for participants who failed screening will not be presented in any summaries or data listings.

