6.1.5. Adverse Events Leading to Study Drug Discontinuation

Treatment-emergent AEs leading to study drug discontinuation will be summarized by SOC and PT and will be presented in a data listing.

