10.4. Exploratory Correlation Analyses

Exploratory correlation analysis will be conducted between selected biomarkers (PGRN, NfL and GFAP) and CDR® plus NACC FTLD Sum of Boxes (FTLD-CDR-SB), for samples collected from both plasma and CSF with baseline and at least one post-baseline measurement in the full analysis population. Summary tables will be provided to show the relationship between each fluid PD biomarker and FTLD-CDR-SB by cohort. The summary tables will include the total number of data points, as well as the Pearson and Spearman correlation coefficients. Scatter plots of actual values for fluid PD biomarkers as the X-axis variable and FTLD-CDR-SB scores as the Y-axis variable will be plotted and will include the Pearson and Spearman correlation coefficients from the summary tables.

A similar but separate analysis to assess the correlations among selected fluid PD biomarker (NfL and GFAP only) levels and quantitative brain imaging parameters MRI (frontotemporal, parietal, and subcortical regions only) will be performed.

Additionally, for the selected fluid biomarkers, the absolute change from baseline to week 49 and percent change over the same interval will be correlated against the absolute change in FTLD-CDR-SB. For selected regional volumetrics (i.e., frontotemporal, parietal, and subcortical regions), the percent change from baseline to week 49 will be correlated with FTLD-CDR-SB scores. The results will be presented in summary tables and scatter plots as described above. Only subjects with both baseline and week-49 biomarker and FTLD-CDR-SB data in the full analysis population will be included.

11. Interim Analysis

No interim analyses are planned for this study.

An iDMC will review safety data during the course of the study to provide recommendations to Alector on study conduct. The details of the iDMC are provided in a separate charter.

12. Changes in the Planned Analysis

Physical and neurological examinations will not be summarized or listed since exam results are only entered on the General Medical History and Baseline Conditions or AE pages of the eCRF.

Due to the high rate of participant attrition over the study duration and small FTD cohort sizes, time points beyond Week 49 will not be included in the cohort level summary of the figures.

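### The SAP has no summary of TEAEs leading to study discontinuation, although the protocol requires one and the SAP keeps the endpoint, and Section 12 does not declare the removal

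*SAP*

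**What the plan says.** SAP section 1.1 names, among the primary safety endpoints in Table 1 (Part 1) and Table 2 (Part 2), "Incidence of treatment discontinuations and study discontinuations due to AEs". Protocol Tables 1 and 2 carry the same item.

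Protocol 8.4.2.4 lists the adverse-event summaries to be reported by SOC, PT and participant group. Two concern discontinuation. One is for stopping study drug; the other is "TEAEs leading to study discontinuation".

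In the SAP, the only discontinuation line in the overview at 6.1.1 is "Any TEAE Leading to Study Drug Discontinuation". Section 6.1.5 then states: "Treatment-emergent AEs leading to study drug discontinuation will be summarized by SOC and PT and will be presented in a data listing". No SAP section plans the counterpart for leaving the study. The nearest coverage is disposition (SAP 3.1), which presents "The number of participants and reasons for study discontinuation, reasons for study drug discontinuation".

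On departures from the protocol, protocol 8.4 says: "Changes from analyses planned in this protocol will be documented in the SAP".

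**The concern.** The SAP keeps an endpoint with two components and plans an adverse-event analysis for only one of them. Section 12 shows that its authors knew how to declare a dropped analysis, so silence here looks more like an oversight than a decision.

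The two components are different quantities in Part 1. Protocol 3.3.1 asks for every effort to follow participants for the full 96 weeks whether or not they stay on drug. Those who stop drug and remain complete an End of Treatment visit; those who leave complete an End of Study visit. How many people left the study because of an AE, and which events were responsible, is a basic tolerability question in a single-arm safety trial. Protocol 1.3.2 treats it as one by reporting that no AE had led to study discontinuation to date. Under the SAP as written, no planned AE table would update that statement.

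**Working it through.** The plan gives no figure for this point, so the check is textual. (Its only computed design figure, the chance of seeing at least one finding in 40 participants, reproduces as 1 − (1 − p)^40 = 3.9%, 33.1%, 87.1% and 98.5% for p = 0.1%, 1%, 5% and 10%. It does not enter the argument.)

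**Step 1. Protocol 8.4.2.4 against the SAP**

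| Protocol summary | SAP counterpart |
|---|---|
| TEAEs | 6.1.1 |
| Treatment-related TEAEs | 6.1.1, 6.1.2 |
| TEAEs by relationship | 6.1.2 |
| TEAEs by severity | 6.1.3 |
| SAEs | 6.1.1, 6.1.4 |
| TEAEs leading to stopping drug | 6.1.1, 6.1.5 |
| TEAEs leading to leaving the study | none |

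Six of the seven have a counterpart. For discontinuation the protocol requires 2 and the SAP plans 1.

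**Step 2. Is the removal declared?** SAP Section 12 declares five changes: examinations ("Physical and neurological examinations will not be summarized or listed since exam results are only entered on the General Medical History" and so on), figures beyond Week 49, apolipoprotein B100, Sortilin in white cells, and several MRI measures. None concerns this table. Declared removals: 0.

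**Step 3. Can the drug-discontinuation table stand in?** In Part 1, AE-driven discontinuation takes three forms:

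- (a) The participant stops drug because of an AE and stays in the study.
- (b) The participant, still on drug, leaves the study because of an AE. Protocol 4.3.2 defines leaving as covering drug and all assessments, so drug stops too.
- (c) The participant has already stopped drug, stays for follow-up, and later leaves because of an AE.

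The planned table would normally show (a) and (b) together, without separating them. For (c) it does not show the event that caused the exit. The required table is (b) plus (c). Events in (c) still qualify as treatment-emergent, because the definition in SAP 6.1 has no cut-off after the last dose. What is lost is therefore the split between (a) and (b), and the exit events in (c).

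**Step 4. Can disposition stand in?** For Part 1, protocol 4.3.2 introduces its list with "The following is a list of possible reasons for study discontinuation" and gives four: withdrawn consent, loss to follow-up, the investigator's judgement, and administrative or other grounds. AE is not named, whereas the list for stopping drug (4.3.1.1) does name a serious or intolerable AE. A count of AE exits is thus not assured. If the form does offer AE as a reason, disposition would give a head count, not treatment-emergent events by SOC and PT.

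**Step 5. Part 2.** Protocol 4.4.1 defines discontinuation as covering drug and all assessments, and its reasons include a serious or intolerable AE, anaphylaxis, liver-enzyme criteria and infusion reactions. The two categories largely coincide, and disposition can show AE as a reason. Little is lost there.

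**The case against.** The best defence is that most of the information survives elsewhere. A participant on drug who leaves because of an AE also stops drug, so the event should appear in the 6.1.5 table. Fatal treatment-emergent SAEs have their own line in 6.1.1. All safety data are to be listed, and with about 40 participants individual cases can be read. This stands as a limit on the size of the problem. It does not supply the missing summary, because a listing is not the table the protocol asks for and 6.1.5 does not separate stopping drug from leaving.

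A reader might infer more than the documents support:

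- **That half of the primary endpoint will go unreported.** Table 1 has ten primary safety items. This is a component of one of them, in a descriptive study without formal testing, and most exits on drug would still show in the drug table.
- **That AE is nowhere a recognised reason for leaving.** That is untrue for Part 2. For Part 1 the list gives only possible reasons and is not the eCRF code list, which is not among the documents.
- **That AE-driven exits are being recorded under withdrawn consent or the investigator's judgement.** Nothing shows this. The SAP's remark about high attrition gives no causes and is used only to limit figures to Week 49.

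**Conclusion.** The point holds as an inconsistency within the plan. A protocol-required AE summary, tied to a primary safety endpoint component that the SAP retains, is absent from SAP 6.1.1 and 6.1.5 and undeclared in Section 12. Label: wrong as written, since the SAP disagrees with the protocol and with its own endpoint table.

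Its weight is moderate and falls mainly on Part 1: the plan would not distinguish those who stopped drug and stayed from those who left because of an AE, and it would miss exit events in people already off drug. The number of participants affected is not in the documents and cannot be estimated from them. The conclusion rests on the SAP text being the full list of planned AE tables. What disposition would actually show depends on an eCRF code list that is not available.

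**What to change.** Add a line for any TEAE leading to study discontinuation to the overview in SAP 6.1.1, and a matching SOC/PT table and listing to 6.1.5. State the data source: the AE page if it records withdrawal from the study as an action, otherwise a link from the AE to the study discontinuation record. The AE data items in protocol 7.5 name no such action, so the derivation should be written down. Because SAP section 2 combines Parts 1 and 2, the table or listing should make Part 1 exits identifiable.

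If the sponsor did intend to drop the summary, Section 12 should say so and give the reason, but the endpoint table would then need to be reconciled as well.

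The cost is one line, one table and one listing. No new data collection is needed if the AE page or the link supplies the attribution.
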